Blood Draws, Pain Testing & Drug Protocol. Figure 3 depicts the timing of blood draws, heat capsaicin procedures, quantitative sensory testing, and drug administration. This protocol will be implemented in the mornings after the US night and the second FA night (FA2). Drs. [name] and [name] have experience conducting all of the pain testing procedures(90-93). Drs. [name], [name], and [name] have extensive expertise studying the effects of opioid agonists(94, 95). All pain testers complete a rigorous training process that includes inter-rater reliability testing ($\kappa > .80$). Participants are permitted to terminate any of the procedures at any time. The following procedures will be conducted in an identical fashion on both visits. All assessments will be conducted by BSMP staff, who will be blind to subject conditions.

Blood Draws & Handling Procedures. Subjects will remain in a semi recumbent position during the procedure. Approximately 30 minutes after Lights On (i.e., wake), the nurse will insert a single port lumen peripheral catheter in an upper extremity vein, contralateral to the arm used for capsaicin testing. A continuous saline infusion at 250cc/h will be maintained. The line will be flushed with saline before and after all blood draws, and will remain installed until the final QST procedure is complete. As shown in Figure 7, seven blood draws will be obtained (3 pre-injection and 4 post-injection). Blood draws 1 and 2 will be obtained approximately 60 minutes apart, prior to the 35 minute heat capsaicin procedure, to provide a resting baseline. After the initial capsaicin procedure, all blood will be drawn prior to each rekindling. Blood will be immediately transported to the Rheumatology Disease Research Core for immediate preparation by the RDRC tech.

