Hypothesis 3.a. (Sleep disruption increases activation of markers of inflammation): We will first compute area-under-the-curve-ground (AUC-G) and -increase (AUC-I) values following standard formulas(134) for the inflammatory markers. AUC allows us to simplify the analysis of the repeated measures data to increase power(134). AUC-G represents the total amount of inflammation during the pre-drug administration segment (blood draws 1-4), whereas AUC-I represents the level of increase in inflammation in response to heat capsaicin (blood draws 3-4), relative to the within-condition baseline levels (blood draws 1 & 2). Mixed effect models will test the difference in marker AUCs between sleep conditions.

Hypothesis 3.b. (Markers of inflammation mediate the effects of sleep disruption on: 1) HA and 2) diminished opioid analgesia): Following the MacArthur approach(135) we will first establish relationships between the markers and both hyperalgesia (HA) and sleep disruption (SD). Thus, these analyses will only be conducted if tests of Hypothesis 3.a. indicate a relationship between SD and activity of a specific marker. For these markers, we will then test the relationship between marker activity and HA using mixed effects models. When significant, interactions between SD and marker activity will be taken as evidence of *mediation* rather than *moderation*, as should a main effect of marker activity after controlling for this interaction and the main effects of SD(135). These analyses use only data from the pre-drug administration segment ;therefore, the placebo and opioid groups are combined. Mixed effects models will test the relationship between marker activity and diminished opioid analgesia, allowing for correlation within individuals across sleep conditions and pre- and post-drug segments. Statistical significance of the main effect of marker activity, the interaction between drug condition and marker activity, or the interaction between drug, marker, and SD will be taken as evidence of a mediating effect of marker activity.

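### Hypothesis 3.b lets a marker main effect alone count as mediation of diminished morphine analgesia, although that term contains no drug contrast

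*Combined protocol and SAP*

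**What the plan says.** Section 7.b, Hypothesis 3.b, names two separate targets: "Markers of inflammation mediate the effects of sleep disruption on: 1) HA and 2) diminished opioid analgesia".

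- **Preliminary steps.** Following the MacArthur approach, "we will first establish relationships between the markers and both hyperalgesia (HA) and sleep disruption (SD").
- **First target (hyperalgesia).** The arms are combined: "These analyses use only data from the pre-drug administration segment".
- **Second target (diminished analgesia).** Mixed models relate the marker to analgesia, "allowing for correlation within individuals across sleep conditions and pre- and post-drug segments". The decision rule lists three alternatives: "Statistical significance of the main effect of marker activity, the interaction between drug condition and marker activity, or the interaction between drug" and the other two factors (the three-way term). A significant result on any one of them "will be taken as evidence of a mediating effect of marker activity". The terms are joined by *or*, with no joint condition.

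Hypothesis 2.a and the Aim 2 power paragraph treat diminished analgesia as a drug effect that differs between sleep conditions.

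The outcome scale, the coding and the marker summary of the analgesia model are not stated. The marker summaries are defined under Hypothesis 3.a: "AUC-G represents the total amount of inflammation during the pre-drug administration segment (blood draws 1-4"). AUC-I likewise treats draws 3–4 as the response to heat-capsaicin. Section 4.a (Blood Draws & Handling Procedures) gives a different count: "seven blood draws will be obtained (3 pre-injection and 4 post-injection"). The Study Design and Heat-Capsaicin paragraphs place the injection after draw 3 and QST1.

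**The concern.** A marker main effect is reasonable evidence for the first target, where the question is whether the marker tracks pain. For the second target the question is whether the marker changes what morphine does. A slope of pain on marker that is the same under morphine and placebo says nothing about that, yet the rule accepts it. One fact, that the marker tracks pain, could then be reported as two findings.

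A marker that raises pain but leaves morphine's effect intact could be published as a reason why poor sleep weakens morphine. The Background (section 3) says such a result would support clinical reports on adding anti-inflammatory drugs to opioids. Aims 1 and 2 and Hypothesis 3.a are not touched.

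**Working it through.** **1. The plan's own figure.** The Aim 3 power paragraph states 80% power at N=80, alpha 0.01, for a marker effect of 0.56. A paired approximation is power = Φ(d/√(2(1−ρ)/80) − z), with z = 2.576. At ρ = 0: 0.56/0.158 = 3.54; 3.54 − 2.576 = 0.966; power 83.3%. At ρ = −0.1 it is 78.8%, at ρ = 0.5 it is 99.3%. The plan does not give its correlations, so 80% can be neither confirmed nor called wrong. That simulation describes marker, sleep and their interaction but no drug term, so the drug-by-marker tests have no stated power.

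**2. What each term can show.** Let pain = βs·S + βd·D + βsd·S·D + γ·M + δ·D·M, with S = sleep disruption, D = morphine and M = marker.

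- *Pre-injection marker.* Randomisation makes M equal on average in both arms. The drug contrast is βd + βsd·S + δ·E(M|S), and γ drops out. If sleep disruption raises M by 0.56 SD, the marker's part in lost analgesia is 0.56·δ. With γ = 0.3 and δ = 0, pain rises by 0.3 × 0.56 = 0.168 SD in both arms and the contribution to lost analgesia is 0.
- *Post-injection marker.* The contrast also contains γ × (drug effect on M), so the marker's part is γ × (drug × SD effect on M). γ is then necessary, but not sufficient without that second factor.
- *Coding.* With arm and sleep coded 0/1, the main effect is the slope under placebo after undisturbed sleep. With effect coding it is the average slope. Neither compares the arms.

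**3. How often the rule misfires: pain level, pre-injection marker.** Inputs from the power section: N=80 (40 per arm), alpha 0.01 (taken to cover Hypothesis 3.b, two-sided), marker raised 0.56 SD, and magnitudes 0.4 (sleep), 0.9 (drug, applied as −0.9) and 0.7 (sleep × drug). Assumed: the marker-to-pain slopes, and a person share of variance of 0.3–0.7 for pain and marker. There is one pre-drug and one post-drug value per sleep condition, with REML mixed models and 2,000 replicates per cell. The true marker effect on analgesia is zero. Entries are the percentage of trials declaring mediation.

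| Coding | Condition | slope 0.1 | slope 0.2 | slope 0.3 |
|---|---|---|---|---|
| Effect coding | both screens also passed | 6–8 | 36–44 | 80–87 |
| Morphine on board, 0/1 | both screens also passed | 4–6 | 20–33 | 53–72 |
| Arm and sleep, 0/1 | both screens also passed | about 2 | 9–15 | 29–46 |
| Effect coding | rule alone | 13–15 | 53–57 | 91–93 |
| Morphine on board, 0/1 | rule alone | 8–11 | 29–42 | 65–81 |
| Arm and sleep, 0/1 | rule alone | 4–6 | 15–21 | 36–50 |

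The screens are a paired sleep–marker test and a pre-drug marker–pain model. Reference points: drug-by-marker terms alone give 2–3% (two independent tests: 1 − 0.99² = 2.0%). A marker unrelated to pain gives 2–4% under the full rule (1 − 0.99³ = 3.0%), or about 1% or less with both screens. A separate implementation (effect coding, person share 0.5, 1,500 data sets) gave 52.5% at slope 0.2 and 91.9% at 0.3 for the rule alone.

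**4. The other readings.**

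- *Pre-to-post change as outcome.* A pure level shift cancels: 2–4%. A marker tied equally to drift in both arms, which is hypothetical, is still flagged: at 0.2, 16–41% (0/1) or 64–96% (effect coding); at 0.3, 39–79% or 96–100%.
- *Post-injection marker, slopes 0.2–0.5, no direct sleep × drug effect.* If morphine does not change the marker, the main effect is significant in 41–100% of trials, and an indirect-path test (both links at 0.01) in 1–2%. If morphine lowers the marker by 0.56 SD after undisturbed sleep and not after disruption (true mediation), the figures are main effect 43–100%, drug-by-marker terms about 2%, indirect-path test 28–89%.

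**The case against.** The strongest reply is that the harm depends on a model the plan does not specify. The text speaks of diminished analgesia, so a change-score outcome is possible, and then a pure level shift is no problem. The drift case that remains is not described anywhere; the power section expects no linear trends within a sleep condition, and section 4.a cites stable hyperalgesia over rekindlings. With post-injection markers the main effect is a needed link, and drug-by-marker terms would miss true mediation. Every marker-to-pain slope is assumed, and with both screens passed the rate in the pain-level reading runs from about 2% to 87%. In that null, the marker does carry part of the sleep effect on pain level, so the error is one of attribution.

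Most of this stands, and it limits how firmly a size can be given. It does not rescue the rule, because under no reading is the main effect sufficient alone. Modelling pre- and post-drug segments together fits pain level better than a change score, though it does not settle the matter. The screens contain no drug contrast, and the marker–pain screen favours exactly the markers that shift pain level. Nor does the MacArthur approach help: it asks for a relation between the marker and the outcome being mediated, which here is a drug effect.

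**Conclusion.** The concern holds: the rule is wrong as written for the second part of Hypothesis 3.b. That the main effect lacks a drug contrast follows from the text and the algebra and needs no assumption. The size does. For a pain-level outcome and a pre-injection marker, with slopes of 0.2–0.3 SD and both screens passed, false mediation is declared in 9–46% of trials with arm and sleep coded 0/1 and 36–87% with effect coding. At slope 0.1 it is 8% or less. Those figures rest on the assumed slopes and variance shares and on alpha 0.01 applying here. The conflict between draws 1–4 as pre-drug and three pre-injection draws is separate, but it decides which analysis is valid. This should be fixed before analysis.

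**What to change.** In section 7.b, Hypothesis 3.b:

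1. Do not accept the marker main effect alone as evidence of mediation of diminished opioid analgesia. Report it as bearing on pain level.
2. State the outcome, the coding and the marker window. Reconcile the pre-drug label on draws 1–4 with the three pre-injection draws in section 4.a.
3. With a pre-injection marker, base the conclusion at alpha 0.01 on drug × marker and drug × marker × SD, with drug meaning morphine on board, or on the equivalent drug × segment × marker terms.
4. If post-injection markers are used, also test the indirect path: the drug × SD effect on the marker together with the marker-to-pain effect.

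The cost is SAP wording and a small analysis change, with no new data. Mediation will be declared less often. For a true drug × marker slope difference of 0.3 SD, power is 42–99% with morphine-on-board terms and 16–80% with drug × segment × marker terms. At 0.2 SD it is 16–74% and 7–36%. The SAP should acknowledge this limit.
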